## 1.0 Introduction

### 1.1 Background

Research evidence has shown that the symptoms of pain, anxiety, depression, and sleeplessness, or any combination of these symptoms are prevalent in patient populations with chronic medical conditions, particularly inflammatory arthritis (Psoriatic Arthritis, Rheumatoid Arthritis), Fibromyalgia, anxiety disorders (PTSD, Generalized Anxiety Disorder), Depression, Chronic Pain conditions (neuropathy, chronic neck and back pain, Osteoarthritis, TMJ Syndrome), and Sleep Disorders. Patients with one of these chronic conditions often have clusters of one or more of these four symptoms (anxiety, depression, pain and sleeplessness).

These patient populations have a need for an innovative treatment approach to address these symptoms, as they often occur simultaneously. By addressing all possible combinations of these symptoms in an individual patient or population, significantly improved outcomes can be achieved.

Globally, the lifetime prevalence of anxiety disorders from a 2013 meta-analysis was 7.3% (4.8-10.9%) and ranged from 5.3% (3.5-8.1%) in African cultures to 10.4% (7.0-15.5%) in Euro/Anglo cultures. This translates into 1 out of 13 and 1 out of 10 people affected globally and in North America respectively. In the United States alone, anxiety affects about 18% of the population or 40 million adults age 18 and older at a cost of more than \$42 billion a year in 1990.

In a separate systematic review on depression, the global prevalence of major depressive disorder was 4.7% (4.4-5.0%). In 2015, over 16 million adults aged 18 or older have been estimated to have had at least one major depressive episode in the prior year representing 6.7% of all U.S. adults.

Insomnia is a global public health issue and is believed to affect approximately 30-35% of the global population. Poor sleep has been associated with decreased immunity, depression, anxiety, poorer quality of life, obesity, increased pain, occupational errors, absenteeism from work, and motor vehicle crashes.

The prevalence of chronic pain, like all the previous conditions discussed, is highly variable by population and other factors. It is estimated that approximately 20% of the adult European population has chronic pain. Similarly, approximately 17.6% (about 40 million) of US adults experience severe levels of pain along with over 11.2% (25.3 million) of adults suffering from daily pain for the prior 3 months at an annual estimated cost of approximately \$560-\$635 billion.

Given the high prevalence of conditions associated with pain, anxiety, depression, and/or sleeplessness (PADS), the associated economic burden, and lack of safe and cost-effective therapies, interest and research is expanding into the field of neuromodulation therapies, including TENS devices, to meet this need.

The Nu-V3 device is not considered to be a Transcutaneous Electrical Nerve Stimulation (TENS) device. TENS devices are applied only in the area of the body directly related to the pain. The Nu-V3 device is placed on the auricular (ear) area and utilizes a non-invasive electrical micro-signal to access the cranial nerves via three small electro-gel pads. There are no TENS devices currently approved or cleared by the FDA that qualify as being substantially equivalent.

Under further research pertaining to accessing the cranial nerves, in particular the vagus nerve, we discovered that there are a variety of Vagal Nerve Stimulators available. However, none are non-invasive and small enough to be attached to the ear while stimulating multiple cranial nerves in the auricular area.

In summary, while Nu-V3 is technically a transcutaneous device, the mechanism for mitigation of symptoms (pain, anxiety, depression and sleeplessness) is unique by TENS standards for the following reasons:

- A. TENS is typically placed in the general area where the pain exists. Nu-V3 is placed only in the auricular area (on the ear) and accesses the cranial nerves as the mechanism for relief.
- B. TENS devices are known to stimulate muscular tissue and nerves in the area where pain exists, creating vasodilation (increased blood flow) and thereby the possibility of temporary relief. Nu-V3, by accessing the cranial nerves (specifically the vagus nerve) non-invasively, acts to stimulate the body's natural enkephalins and elevate blood flow, and may result in the balancing or rebalancing of the Autonomic Nervous System (ANS).
- C. By accessing the cranial nerves in the manner described above, the effect may be cumulative and residual and offer the patient immediate, intermediate and longer lasting results and relief.

For the reasons cited above, Nu-Life will be submitting Nu-V3 for FDA clearance under De Novo 513(f)(2), as a new and unique technology. In part, the purpose of this clinical study is to demonstrate the effect upon the four specific symptoms of pain, anxiety, depression and sleeplessness, as any one or combination of these symptoms may result in Autonomic Nervous System dysfunction.

## 1.2 Device Description

The Nu-V3 device is a miniaturized, wearable, microchip-controlled, cranial nerve stimulation treatment device, which delivers pulsed micro-signals over a period of 14 days. The Nu-V3 device provides a continuous flow of intermittent, low frequency electrical pulses to the ear's specific cranial nerve endings. The Nu-V3 device is a patent pending, non-invasive transcutaneous stimulating device which offers useful features to the patient and clinical professional. The Nu-V3 device control features are set by the manufacturer and prevent patient misuse of the device. Three miniature, non-invasive, electro-gel pads are utilized to deliver a micro signal at 1

Hz in a square plus minus waveform, which cycles on and off every three hours to provide a resting period and prevent adaption to the stimulation. The device is powered by three (No.10) zinc air batteries at 1.4 volts each, 4.2 volts in total, to provide the required stimulation for up to 14 days. The low frequency, reliability of the zinc air batteries and consistency of the micro-signal through the eight-pin micro-chip technology, provides consistent and equivalent stimulation energy regardless of individual skin impedance.

### 1.3 Non-significant Risk Medical Device Study

The FDA considers other microcurrent transcutaneous devices (such as TENS devices) as nonsignificant risk devices for medical device studies. The Nu-V3 device used in this study reflects an investigational device that meets the definition of a nonsignificant risk device per review of the IRB.

## 2.0 STUDY OBJECTIVE

The objective of this research study is to collect data which demonstrates the ability of the Nu-V3 device to offer relief from one or more of the following symptoms: pain, anxiety, depression, and/or sleeplessness. The objective is to demonstrate the effectiveness of Nu-V3 for any or all of the four symptoms listed.

## 3.0 STUDY PARTICIPANT SELECTION CRITERIA

### 3.1 Inclusion Criteria

- Participant is at least 18 years of age
- Participant presents with one or more of the following symptoms: pain, depression, anxiety, and/or sleeplessness
- Participant is capable of understanding the use and maintenance of the device
- Participant is capable and agreeing to participate in the ongoing assessment
- Participant has signed the Informed Consent Form
- Participant can commit to follow all protocol study timepoints

### 3.2 Exclusion Criteria

- Participants with a Pacemaker
- Participants with irregular heart rate or a heart rate lower than 60 beats per minute (bradycardia)
- Have had a transplant within the last 2 years
- Have had a heart attack or cardiac bypass surgery within the last 12 months
- History of substance abuse, including prescription drugs, within the last 12 months
- Patients with complaints of dizziness or lightheadedness within the last 3 months
- Women who are pregnant

- Participants with Diabetic Retinopathy
- Current Ear infection
- SBP < 100 and/or DBP < 60
- History of uncontrolled bipolar disorder within the last 12 months
- History of uncontrolled seizures within the last 12 months
- History of Aneurysms
- History of syncope within the last 12 months
- Participants that have had a TIA or stroke within the last 12 months
- Participants with health problems deemed at risk for the study by the Principal Investigator
- Participants with any changes to Pain/Anxiety/Depression/Sleeplessness medications within last 60 days (participants that do not meet this medication-change washout period may be delayed until 60-day period is met)
- Participants that are currently under adjudication process for disability support, VA or other

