**Nu-Life Products, Inc**

Manufacturing and Supply of Nu-7

**Important:** Before applying the device, read all use and safety instructions on the reverse side.

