### SAFETY INSTRUCTIONS

These safety instructions are an integral part of the Nu-V3 and the therapy provided by the device and as such, must be followed closely to ensure the proper use of the device and safety of the treatment. These instructions for use and safety instructions are to be read and observed in full by every user. Treatment Provider and patient are both responsible for educating themselves and following these instructions and the proper use of the device as described in these instructions. Non-observance of the warnings and safety instructions may lead to injuries, infections or serious harm to the user and others.

The exclusive PADS™ assembly is only intended for single use. The re-use of single-use products represents a possible risk for the patient or user. Never place the exclusive gel pads on any location other than the auricular (ear) area, especially the eyes. It is important that all used devices and PADS™ assemblies are not reused in any way and that the device and PADS™ assembly is removed by the treatment provider or returned to the treatment provider by the patient or user.

Use of the device in the immediate vicinity of short-wave, or RF devices can be a cause of interference and should be avoided. The serial number for the Nu-V3 device is located on the packing for each device. These serial numbers are kept on file with the manufacturer and should be kept by the treatment provider and filed with the patient's reports on a regular basis.

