### Absolute Contraindications

- History of dizziness or lightheadedness within the last 30 days
- Current ear infection
- Heart rate lower than 60 beats per minute (bradycardia)
- SBP < 100 and/or DBP < 60
- Heart attack within the last 12 months
- Cardiac bypass surgery within the last 12 months
- History of uncontrolled seizures
- Aneurysms
- History of an organ transplant within the last 2 years
- Pregnancy
- Diabetic Retinopathy
- Uncontrolled Bipolar Disorder within last 12 months

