### TECHNOLOGY DATA

Appliance: Non-invasive, Pulsed Stimulation Device Type description: Nu-V3 Device Power supply: 3 X 1.4 V batteries (Type AC 10E)  
Output: (Load impedance range 1k-10kΩ) max. 3.8V, Impulse interval 500ms, Impulse width 5ms, (1Hz / 5 ms / bipolar), max duration of treatment 14 x 24 hours.  
Classification: Class II (FDA) Duty Type: approx. 3h duty / 5h at rest (periodic duty) Weight incl. battery: .20 oz. Dimensions: 1.25 in x .5 in.

Form 0110001

The Nu-V3 Device

For professional use only

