### Medical History Form

Please answer the following questions about your past and current medical history.

1. Do you have a history of any significant medical problems or chronic disease requiring a physician's care?

Yes (If Yes, please list below)     No

Medical Problem	Date of Diagnosis (dd/mmm/yyyy)	Are you having trouble with this problem now?
	/ /	 Yes  No
	/ /	 Yes  No
	/ /	 Yes  No
	/ /	 Yes  No
	/ /	 Yes  No
	/ /	 Yes  No
	/ /	 Yes  No
	/ /	 Yes  No
	/ /	 Yes  No
	/ /	 Yes  No

2. Have you had trouble with or sought medical attention for (please include even if stated in Question 1).

Irregular Heart Rate	 Yes  No	
Cardiac Arrhythmia	 Yes  No	
Heart Disease	 Yes  No	

Nu-Life Solutions  
Version Date: October 30, 2017

Subject ID \_\_\_\_\_ Date (dd/mmm/yyyy): \_\_\_\_/\_\_\_\_/\_\_\_\_

Chest Pain	 Yes  No	
Heart Attack	 Yes  No	
Heart Murmur	 Yes  No	
Dizziness/ Lightheadedness	 Yes  No	
Diabetic Retinopathy	 Yes  No	
Bradycardia	 Yes  No	
Epilepsy, Seizures, or Convulsions	 Yes  No	
Aneurysms	 Yes  No	
Syncope	 Yes  No	
TIA or Stroke	 Yes  No	
Drugs or Alcohol	 Yes  No	

3. Have you had trouble with or sought medical attention for (please include even if stated in Question 1).

High Blood Pressure	 Yes  No	

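### The seizure exclusion looks back only 12 months, while the device leaflet bars any history of uncontrolled seizures, so the written criteria can admit someone the device's own instructions rule out.

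*Protocol*

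**What the plan says.** The trial's seizure rule appears in three places with the same limit. Protocol section 3.2, the Appendix 4 eligibility checklist and the SAP eligibility summary each exclude "History of uncontrolled seizures within the last 12 months".

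Protocol Appendix 6, the use and care leaflet for patients, has a list headed Absolute Contraindications. Its seizure entry reads "History of uncontrolled seizures" and stops there. The same list does give a period for other conditions, for example "Uncontrolled Bipolar Disorder within last 12 months". The leaflet's safety section says the instructions "must be followed closely to ensure the proper use of the device and safety of the treatment", and it makes the treatment provider and the patient both responsible for following them.

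Three other provisions bear on the point:

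- Section 3.2 and the checklist also exclude "Participants with health problems deemed at risk for the study by the Principal Investigator".
- The Appendix 8 medical history form asks about "Epilepsy, Seizures, or Convulsions" without a time window.
- The Appendix 5 instructions tell the person fitting the device: "Before applying the device, read all use and safety instructions on the reverse side".

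**The concern.** The checklist is the working tool for enrolment. On its seizure line, a site that follows it exactly records a past history of uncontrolled seizures as no bar once 12 months have passed. The leaflet for the same device treats that history as an absolute contraindication. The participant would then wear the device round the clock through eight weeks of treatment, holding instructions that say they should not use it.

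The issue is participant safety and consistency between sites. In a multi-center study with two conflicting texts, one site may enrol such a person and another may turn them away, each with a document to support the decision. No endpoint, sample size or error rate is affected.

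**Working it through.** The plan states no figure on this point, so the check compares wording. Each absolute contraindication in Appendix 6 is set against section 3.2.

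| Leaflet item (Appendix 6) | Leaflet window | Section 3.2 | Trial relative to leaflet |
|---|---|---|---|
| Dizziness or lightheadedness | 30 days | 3 months | stricter |
| Ear infection | current | current | same |
| Heart rate below 60 | none | same, plus irregular rate | same or stricter |
| Low blood pressure | none | same thresholds | same |
| Heart attack | 12 months | 12 months | same |
| Cardiac bypass | 12 months | 12 months | same |
| **Uncontrolled seizures** | **none** | **12 months** | **looser** |
| Aneurysms | none | any history | same or stricter |
| Organ transplant | 2 years | 2 years, any transplant | same or stricter |
| Pregnancy | none | excluded | same |
| Diabetic retinopathy | none | excluded | same |
| Uncontrolled bipolar disorder | 12 months | 12 months | same |

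**Count.** Same or stricter on 11, looser on 1; 11 + 1 = 12.

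**Does the missing window mean any time in the past?** Five of the 12 leaflet items state a look-back period: dizziness, heart attack, bypass, transplant and bipolar disorder. The list therefore gives a period where one is meant. Aneurysms, the other past-history item with no leaflet window, is carried into section 3.2 as any history. Read the same way, the seizure entry covers any past uncontrolled seizures.

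**Is the looser rule a deliberate policy?** Nothing in the text supplied gives a reason for it, and the general pattern runs the other way. Section 3.2 excludes outright anyone with a pacemaker, or with syncope, TIA or stroke in the last 12 months. The leaflet lists all of these as relative contraindications only.

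**Test case.** Take a candidate whose last uncontrolled seizures were 18 months before screening.

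- Seizure line in section 3.2, the checklist and the SAP: 18 > 12 months, so not excluded.
- Leaflet: a history of uncontrolled seizures exists, so absolutely contraindicated.

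The two rules give opposite answers for every candidate whose uncontrolled seizures ended more than 12 months before enrolment. Someone whose epilepsy has always been well controlled is barred by neither.

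**The case against.** The strongest reply is that the leaflet cannot be binding when it creates the conflict and powerless when it could resolve it. If the instructions must be followed, they apply at device placement. The fitter has to read them first, so the likely outcome is a late screen failure and not treatment. In addition, the investigator-judgement item is a required answer on the same checklist, above which the investigator signs a statement of eligibility, and the history form will have brought the old seizures to light. Enrolment would need the investigator to judge this person not at risk with both facts available.

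That argument lowers the probability but does not remove the gap. Answering the judgement item is compulsory, but what to answer is left open and no condition is named. A yes on the history form triggers no stated exclusion. Reading the leaflet at placement reveals the contradiction without saying which document prevails, and a screen failure after consent and registration is a poor way to discover it.

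Three further points stand in part:

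- The process maps are figures missing from the text available, so it can be said only that no rule linking seizure history to exclusion appears in the readable text.
- Nothing shows which text is in error. The trial's 12 months matches its own bipolar, syncope and TIA or stroke windows, so a phrase dropped from the leaflet is plausible. Under either explanation one text needs correcting.
- The affected group is narrow and the analysis is untouched, which limits the weight of the point without making the texts agree.

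**Conclusion.** The concern holds. On one of 12 absolute contraindications the trial's written criterion is looser than the device's own instructions, and the existing safeguards reduce the chance of a contraindicated enrolment without preventing it.

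The conclusion assumes that the unqualified leaflet entry means uncontrolled seizures at any time, which the rest of the list supports. It is confined to past uncontrolled seizures. The number of candidates concerned is not given and cannot be derived from the documents; with 50-100 participants planned it is probably small. Confidence in the mismatch itself is high, because it rests on the wording of the texts. This should be corrected before enrolment on safety grounds; it has no bearing on the statistical analysis.

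**What to change.** Before enrolment, delete the 12-month limit from the seizure exclusion in Protocol section 3.2, the Appendix 4 checklist and the SAP eligibility summary, so that the trial is at least as strict as the leaflet. If the sponsor and clinicians confirm that 12 months is safe, keep the trial wording and add that limit to the seizure line in Appendix 6. The choice of window is clinical; what matters here is that all four places agree.

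The cost is one phrase in three texts, or one phrase in the leaflet, with IRB approval of the revised documents. Removing the limit may make a few candidates ineligible. No visit, procedure or analysis changes.

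A separate clerical point can be settled in the same revision. The technical data in Appendix 6 give a cycle of about 3 hours on and 5 at rest (24 × 3/8 = 9 hours a day). Section 1.2, Appendix 5 and the Appendix 6 remarks give 3 on and 3 off (24 × 3/6 = 12 hours a day). The line should be checked against the device specification. The discrepancy does not show that the delivered stimulation differs.

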## 4.0 STUDY PROTOCOL

The Nu-V3 Clinical Study is a prospective, single-arm, open-label, multi-center study using the Nu-V3 cranial nerve stimulation treatment device in patients with pain, anxiety, depression, and/or sleeplessness.

For this Phase I study, a total of 50-100 patients at multiple centers will be registered for study participation. Study participants are those who have signed the informed consent form, met the inclusion and exclusion criteria, and are enrolled in the study at one of multiple sites. Enrolled participants are stratified based on their pain, anxiety, depression, and/or sleeplessness symptom presentation at baseline and treated with the Nu-V3 device for 8 weeks, then observed for an additional 4 weeks. Interim analysis of reported data will be based on baseline stratifications and conducted at 4, 8, and 12 weeks during this time. Post study, participants will be given the chance to continue with an optional maintenance treatment with the Nu-V3 device per a 2-weeks on, 2-weeks off schedule, for an additional 12 weeks, with an 8-week observation.

Subjects enrolled onto the Nu-V3 Clinical Trial will undergo the following regimen:

- At the baseline visit, patients will be asked to complete study questionnaires (Appendix 11) regarding all of the following symptoms: pain, anxiety, depression, and/or sleeplessness, as well as their quality of life, active medications, medical history, and demographical information.
- At each subsequent visit, patients will be asked to complete study questionnaires regarding all the following symptoms: pain, anxiety, depression, and/or sleeplessness, as well as their activity level and quality of life.
- The sessions will begin with the Nu-V3 device being placed on the left ear and three small pads (non-invasive) being placed on the ear. Each Nu-V3 device

lasts for up to 14 days with a change in the pads approximately 7 days into the treatment.

- Each session takes approximately 15-20 minutes. The placement of the device takes approximately 5 minutes and the remaining time is spent verifying ePRO form completion, and evaluating the patient for all device effects.
- The Nu-V3 device is mobile and is worn externally on the left ear 24 hours a day during treatment, fitting comfortably behind the ear. An electrical signal is sent to the external ear through coated wire leads attached to the device and adhesive pads which attach to three sites on the ear.
- Participants should be able to perform their typical day-to-day activities while wearing the device. They may shower while wearing the Nu-V3 device, provided that they do not get the device wet and use the small disposable ear covers that are provided for them.
- Patients should not change their existing forms of treatment or medications without discussion with the investigator.
- Nu-Life reserves the right to capture video, photographs and written testimonials from patients with written permission. In the event subjects elect to participate in any or all of these activities, they will be asked to sign a waiver giving exclusive rights to Nu-Life for the materials gathered from the patient, such as video, photographs and written testimonials. Their participation in this study is not dependent upon their willingness to provide these testimonial materials.

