#### 4.1 Phase I Study Assessment Tables

Nu-Life Solutions Miniaturized Wearable Medical Technology - Nu-V3		Study Treatment Assessments Table										Nu-V3
		*Evaluations are completed weekly, every 7 days =3 days										
Evaluation*	Study Treatment											
	Week 1	Week 2	Week 3	Week 4	Week 5	Week 6	Week 7	Week 8	Week 9-11	Week 12		
Informed Consent	x											
Inclusion and Exclusion 	x											
Patient Registration 	x											
Medications Form 	x			x				x		x		
Patient Onboarding and Orientation 	x											
In office assessment	x	x	x	x	x	x	x	x		x		
New Device Placed	x		x		x		x					
Pad Replaced		x		x		x		x				
Treatment Forms 	x	x	x	x	x	x	x	x				
No Device									x	x		
ePRO Questionnaires 	x	x	x	x	x	x	x	x	x	x		
Patients' Global Impression of Change ePRO form (PGIC) 		x	x	x	x	x	x	x		x		
Providers' Global Impression of Change ePRO form (PGIC)		x	x	x	x	x	x	x		x		
Family Global Impression of Change ePRO form (PGIC)		x	x	x	x	x	x	x		x		
Optional Patient Media Testimony	x			x				x		x		

1. Inclusion/Exclusion, Registration, Medications, Treatment forms to be completed by site coordinator via online module.  
 2. Patient Onboarding and Orientation includes introductory demographics form, Nu-V3 patient training video  
 3. ePRO questionnaires completed on patient's mobile device: DQ-9 (baseline), PTB-7, PEG, GAD-7, PHQ-9, PROMIS 4a, PGIC  
 4. If patient consents to media testimony, site will collect via study collection process every 4 weeks.

Evaluation*	Post Study Intervention Assessments Table														
	*Evaluations are completed weekly, every 7 days ±3 days														
	Optional Maintenance Therapy										Long Term Follow Up				
Week 13	Week 14	Week 15-16	Week 17	Week 18	Week 19-20	Week 21	Week 22	Week 23	Week 24	Week 25	Week 26	Week 27-28	Week 29	Weeks 30-31	Week 32
Medications Form 				x			x			x					x
In office assessment	x	x		x	x		x	x							
New Device Placed	x			x			x								
Pad Replaced		x			x			x							
Treatment Forms 	x	x		x	x		x	x							
No Device			x			x			x	x	x	x	x	x	x
ePRO Questionnaires 	x	x		x	x		x	x	x	x		x			x
Patients' Global Impression of Change ePRO form (PGIC) 	x	x		x	x		x	x				X			X
Providers' Global Impression of Change ePRO form (PGIC)		x			x			x				X			X
Family Global Impression of Change ePRO form (PGIC)		x			x			x				X			X
Optional Patient Media Testimony		x			x			x				x			X

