## 5.0 DATA COLLECTION AND RETENTION

The study endpoints data will be collected from each participant's study questionnaires. The data will be collected electronically via the patient's own device, and uploaded to an electronic data capture system. Only patient data from the stratified indication(s) will be used for analysis of symptom response. The data will be used to demonstrate that the Nu-V3 device provides participants with relief of the symptoms of pain, depression, anxiety and/or sleeplessness. The data analysis will include comparative data for each participant's questionnaire prior to beginning treatment with the Nu-V3 device, the participant's weekly questionnaires during

treatment and the questionnaire completed at the end of the treatment with the Nu-V3 device.

Interim analyses of available data will be regularly submitted to the FDA for review.

The Principal Investigator at each site will be responsible for recording, collecting, and storing the research participant's study data. The written records must be stored in a secure location. Only the Principal Investigator or designated study staff will have access to the study records and all electronic files will be password protected. The Principal Investigator will also maintain adequate records for the study including:

- all correspondence with the IRB and Sponsor
- other pertinent data related to the study

All records are to be retained by the Principal Investigator for a period of seven (7) years following the closure of the study. Following study closure, the Principal Investigator shall inform Nu-Life of the location of study records and storage changes (i.e. the Principal Investigator leaves the institution where the study was conducted). In such cases, the study records may be transferred to another institution, investigator, or to Nu-Life upon written agreement between the Principal Investigator and Nu-Life.

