**NU-V3 WEEKLY VISIT PROCESS MAPS**

**Weeks 2-8**

**Weeks 9-12**

## Appendix 4: Eligibility Checklist

**NU-V3 Protocol No. 1**

### SCREENING AND ELIGIBILITY CHECKLIST

A Single-Arm, Phase I Study to Evaluate the Efficacy of the Nu-V3 Device for Patients with Pain, Anxiety, Depression, Sleeplessness

Subject Initials:
Subject Identification Number:
Date of Consent:

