## PHQ-9- Patient Health Questionnaire

Subject ID: \_\_\_\_\_ Date (dd/mmm/yyyy): \_\_\_\_/\_\_\_\_/\_\_\_\_

Over the last 2 weeks, how often have you been bothered by any of the following problems?  
(use "✓" to indicate your answer)

	Not at all	Several days	More than half the days	Nearly every day
1. Little interest or pleasure in doing things	0	1	2	3
2. Feeling down, depressed, or hopeless	0	1	2	3
3. Trouble falling or staying asleep, or sleeping too much	0	1	2	3
4. Feeling tired or having little energy	0	1	2	3
5. Poor appetite or overeating	0	1	2	3
6. Feeling bad about yourself—or that you are a failure or have let yourself or your family down	0	1	2	3
7. Trouble concentrating on things, such as reading the newspaper or watching television	0	1	2	3
8. Moving or speaking so slowly that other people could have noticed. Or the opposite — being so fidgety or restless that you have been moving around a lot more than usual	0	1	2	3
9. Thoughts that you would be better off dead, or of hurting yourself	0	1	2	3

add columns  +  +

(Healthcare professional: For interpretation of TOTAL, please refer to accompanying scoring card). TOTAL:

10. If you checked off any problems, how difficult have these problems made it for you to do your work, take care of things at home, or get along with other people?	Not difficult at all _____ Somewhat difficult _____ Very difficult _____ Extremely difficult _____
---	---

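### No readable step directs anyone to read PHQ-9 item 9; the gap is clearest where ePRO forms fall due without an office visit

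*Protocol*

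**What the plan says.** **Collection.** Protocol section 4.0 asks every participant for questionnaires on all four symptoms, whatever their stratum. The footnote to the section 4.1 schedule lists the packet: "ePRO questionnaires completed on patient's mobile device: DQ-9 (baseline), PTB-7, PEG, GAD-7, PHQ-9, PROMIS 4a, PGIC". Item 9 of the PHQ-9 in Appendix 11 reads "Thoughts that you would be better off dead, or of hurting yourself" and is scored 0 to 3. Section 5.0 gives the route: "The data will be collected electronically via the patient's own device, and uploaded to an electronic data capture system".

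**Reading.** For the weekly session, section 4.0 says that after device placement "the remaining time is spent verifying ePRO form completion, and evaluating the patient for all device effects". The SAP's description of the session is similar: form completion and immediate device effects. The PHQ-9 form carries one note to staff: "Healthcare professional: For interpretation of TOTAL, please refer to accompanying scoring card". It sets no deadline. Section 5.0 adds "The Principal Investigator at each site will be responsible for recording, collecting, and storing" the study data, and "Only the Principal Investigator or designated study staff will have access to the study records".

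**Reporting.** Section 7.0 starts from an unanticipated problem. The sponsor must be told within 24 hours and the central IRB within 5 calendar days, and the form is due within 10 calendar days. No questionnaire answer is named as a trigger.

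**Schedule.** In the section 4.1 treatment table, repeated in the SAP, the ePRO row is marked in every column. The in-office row is marked for Weeks 1-8 and Week 12 and is blank for Weeks 9-11. Treatment Forms and the provider's rating are also blank for Weeks 9-11.

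**The concern.** A trial that enrols patients with depression and asks them repeatedly about self-harm should say who reads the answer and how soon. Checking that a form is complete is not the same as reading it. In weeks without a visit, the answer goes from the patient's device to the database, and the readable text requires no clinician to look at it.

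The stake is participant safety. A positive item 9 may be an expected symptom and is not automatically an unanticipated problem. Until someone reads it, though, the investigator cannot decide on a clinical response, on withdrawal by physician decision (listed under Accountability in the SAP), or on reportability under section 7.0.

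**Working it through.** The plan states no delay figure, so there is none to reproduce. The check has five steps.

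**1. Does any readable step lead to item 9?**
- Session task (section 4.0): completion and device effects, not answers.
- PHQ-9 note (Appendix 11): the total only. With nine items scored 0-3 the total runs to 9 × 3 = 27. A patient who scores 3 on item 9 and 0 elsewhere has a total of 3 out of 27, so reading the total does not amount to reading item 9.
- Section 7.0 and the SAP safety section: no questionnaire trigger.
- Interim analyses (section 4.0): Weeks 4, 8 and 12. They analyse symptom data and none falls within Weeks 9-11. Section 5.0 limits the symptom-response analysis to a patient's stratified indications, so the PHQ-9 of a patient stratified only to pain is not used there.

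The result is that no such step was found in the readable text.

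**2. Nominal interval from form to Week 12 visit.** With weekly spacing, the interval is (12 − w) × 7 days.
- Week 9: (12 − 9) × 7 = 21
- Week 10: (12 − 10) × 7 = 14
- Week 11: (12 − 11) × 7 = 7

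If the single Week 9-11 cell means one form, the interval lies somewhere from 7 to 21 days.

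**3. Visit window.** The window is read as ±3 days, as printed over the extension table (the sign is garbled over the treatment table). Applied to both dates it adds ±6 days: 15-27, 8-20 and 1-13 days.

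**4. Extension table.** It has 16 week headings against 15 cells per row, so marks cannot be assigned to weeks. By cell order alone, in-office marks are in cells 1, 2, 4, 5, 7 and 8, and ePRO marks are in those cells plus 9, 10, 12 and 15. Four ePRO marks therefore follow the last in-office mark. A provider rating is marked alongside two of them (cells 12 and 15) but not the other two.

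**5. A one-business-day reading limit, for comparison.** It gives 1 calendar day midweek, 3 from Friday to Monday, and 4 from Friday to Tuesday with a Monday holiday.

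**The case against.** The strongest objection is that the most relevant pages cannot be read. Appendix 3 sets out the weekly workflow, and its figures are missing from the text available for review, including the map for Weeks 9-12. The scoring card and consent pages are missing too. Any of these may contain the step. This stands, and it limits the finding to the readable text.

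The Weeks 9-12 map also sits under the heading "NU-V3 WEEKLY VISIT PROCESS MAPS", so some contact in Weeks 9-11 is possible even though the schedule marks no in-office assessment. This stands as well.

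A reader might infer from the schedule that a positive answer will go unread for 7 to 21 days. The documents do not support that. Section 5.0 gives site staff access and makes the investigator responsible for collecting the data, so earlier reading is neither required nor ruled out. Nor does Week 12 guarantee an end to the wait, because that visit is not directed to item 9 either. It would also be too strong to claim a minimum saving from a reading limit. With the visit window, a Week 11 form can fall 1 day before the Week 12 visit, so a limit of 1 to 4 days might save nothing.

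Existing safeguards deserve credit. Section 3.2 excludes recent uncontrolled bipolar disorder and recent relevant medication changes, and lets the investigator exclude patients judged at risk. The Medical History Form asks about psychiatric hospitalisation and diagnoses. Office assessments in Weeks 1-8 and provider ratings in Weeks 2-8 give staff further chances to notice a problem. These lower the risk, but none requires item 9 to be read during follow-up.

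**Conclusion.** The point holds for the readable text: every patient answers item 9 in every packet, and no visible step directs anyone to read it. The gap is clearest in Weeks 9-11 and at the extension forms that follow the last in-office mark. The documents do not show which of these is worse.

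The 21, 14 and 7 days show how far apart form and visit are scheduled. They are not a delay that the plan sets or predicts.

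A reader might also infer that section 7.0 deadlines would be missed, because all three nominal intervals exceed 5 days. That does not follow: those limits run from a reportable event, and a positive item 9 is not automatically one.

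This should be fixed for participant safety. Confidence is medium, because Appendix 3 may already contain the step. No endpoint analysis is affected.

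**What to change.** First check Appendix 3. If its maps already contain an item 9 review, refer to it in sections 4.0 and 7.0. Otherwise amend sections 4.0 and 4.1:

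1. Flag any item 9 answer of 1 or more to the site investigator or a designee, with a named back-up, on upload. Apply this to every packet and stratum, including weeks without a visit. If the system cannot send alerts (section 5.0 does not say), have designated staff check uploads on a schedule.
2. Require the answer to be read within a stated time, such as one business day. Patient contact and a clinical risk assessment then follow at the investigator's judgment, and both review and action are recorded. Reportability is then judged under section 7.0.
3. Change the visit task to verifying completion and reviewing item 9.

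The cut-off and the time limit are proposals; the documents give neither. A score of 1 is the lowest answer above the zero category on the printed form.

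The cost is a short amendment, one alert rule or a routine manual check, and a small workload for existing staff. The downside is some alerts for stable, low-level answers. Their number cannot be estimated from the documents.
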